### 8.2 Setting and Study Population

### 8.2.1 Study Period

The study period will be from 17 May 2018, which is the date of US FDA approval for erenumab-aooe, to 31 May 2020 (or the latest release date for the MarketScan® claims database).

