### 8.2.2.1 Inclusion Criteria

Patients must meet the following inclusion criteria:

- 1. 18-64 years of age on the index date.
- 2. One year of continuous enrollment (ie, complete medical and pharmacy coverage) prior to and including the index date, which defines the baseline period.
- 3. A diagnosis of migraine during the baseline period, based on one of the following criteria:
  - a) ≥1 inpatient claim with a diagnosis of migraine (ICD-10-CM) diagnosis code of G43.xxx).
  - b) ≥1 outpatient evaluation and management claim with a diagnosis of migraine and a specialty code of 260 (neurologist).
  - c)  $\geq 1$  claim for emergency room visit with a diagnosis of migraine.
  - d) ≥1 outpatient evaluation and management claim with a diagnosis of migraine PLUS ≥1 pharmacy fill for a migraine-specific triptan or an ergotamine class medication within 365 days of each other
  - e) ≥2 outpatient evaluation and management claims with a diagnosis of migraine between 7 and 365 days apart.
  - f) ≥2 pharmacy fills for migraine-specific triptans or ergotamine class medications between 7 and 365 days apart.

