#### 8.3.4 Validity and Reliability

We will use validated definitions where appropriate to identify the cardiovascular events that are of interest in this study (Sentinel Initiative, 2018; McCormick et al, 2015; Sherman et al, 2013; Cutrona et al, 2013; Tirschwell and Longstreth, 2012; Quan et al, 2009; Roumie et al, 2008; Tu et al, 2007; McCormick et al, 2015).

The primary algorithm, with a positive predictive value (PPV) of 86% (95% CI: 79%, 91%), to identify acute MI requires an ICD-10-CM diagnosis code of I21.xxx or I22.xxx (see Appendix C) in the principal or primary position of facility claims for hospitalization (Cutrona et al, 2013).

As with acute MI, an algorithm to identify ischemic stroke with good PPV (90% [95% CI: 77%, 97%]) also requires an ICD-10-CM diagnosis code (I63.xxx) occurring in the primary position for facility claims for hospitalization (Tirschwell and Longstreth, 2012). In contrast, the algorithms for intracerebral hemorrhage (PPV – 89% [95% CI: 75%, 99%], ICD-10-CM diagnosis code I61.xxx) and subarachnoid hemorrhage (PPV – 94% [95% CI: 83%, 99%], ICD-10-CM diagnosis code I60.xxx) require a diagnosis code for hemorrhage that can occur in any diagnosis position for an inpatient hospitalization (Tirschwell and Longstreth, 2012). All ischemic and hemorrhagic (intracerebral and subarachnoid) stroke events will be combined to identify 'any stroke' for the primary analysis; however, the cumulative incidence of ischemic and hemorrhagic stroke events will also be described separately.

Algorithms that evaluate acute MI, ischemic stroke, and hemorrhagic stroke in either the emergency room (ER) or the inpatient setting will also be considered.

There are a number of algorithms, with varying performance characteristics, to identify clinical hypertension in administrative claims data (Sherman et al, 2013; Quan et al, 2009; Tu et al, 2007) but none to evaluate drug-induced hypertension. As a result, using the hypertension codes listed in Appendix C, we will evaluate new onset hypertension with the following algorithms:

- 1. 1 IP / 1 ER / 1 OP diagnosis (any position) of hypertension
- 2. 1 IP / 1ER / 1 OP diagnosis (any position) of hypertension, with a prescription fill for an anti-hypertensive medication within 30 days after the hypertension diagnosis date.
- 3. 1 IP / 1ER / 1 OP diagnosis of hypertension (any position), and discontinuation of the study medication within 90 days after diagnosis

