- 4. 1 IP / 1 ER / 1 OP diagnosis (any position) of hypertensive crisis
- 5. 1 IP / 1 ER diagnosis of hypertension in the primary position

New onset hypertension will be the primary hypertension outcome of interest, and the cumulative incidence of this outcome will be evaluated at 1 month, at 2 months, at 3 months, at 6 months, and at 12 months. When evaluating new onset hypertension, individuals with a prior history of hypertension during the baseline period will be excluded. For individuals with baseline hypertension and anti-hypertension medication use, we will also evaluate changes in medication dosage or initiation of new anti-hypertensive medications within 90 days after initiation of the study medication.

In addition, we will evaluate the occurrence of a single diagnosis of elevated blood pressure reading, without diagnosis of hypertension (ICD-10-CM diagnosis code R03.0) occurring in any diagnosis position in the IP, ER, or OP setting.

The algorithm used to identify patients with migraine in this study has not been validated, but a similar algorithm (Kolodner et al, 2004) had high specificity and low sensitivity. Thus, it is possible that some migraine patients will be misclassified as non-migraine patients and will be excluded from this study.

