#### 8.5 Study Size

Based on recent analyses (Amgen Study 20200218) to evaluate the rate of hypertension in migraine patients, the following number of patients with a migraine preventive treatment were identified within the Marketscan® Early View claims database from May 2018 through January 2020:

- 15212 erenumab-aooe users
- 17239 galcanezumab-gnlm or fremanezumab-vfrm users
- 9242 onabotulinumtoxinA users

These migraine preventive treatment users were required to be 18-64 years of age, have a diagnosis for migraine based on ICD-10-CM diagnosis codes or one prescription order for a triptan/ergot in the prior 12 months, continuous enrollment in the claims database for at least 12 months prior to the index date, and no prior prescription for any medication targeting the CGRP pathway. These counts were generated before the February 2020 approval of eptinezumab-jjmr. Assuming a conservative 3-month growth rate of 15%, the expected number of new users during the study period (17 May 2018 – 31 May 2020) will be ~20 000 new users of erenumab-aooe, ~23 000 new users of other mAbs targeting the CGRP pathway, and ~13 000 new users of onabotulinumtoxinA. While new users of the SOC migraine preventive medications (anti-epileptics) were not evaluated, other analyses in the Optum electronic health record database suggest that this new user cohort will be at least as large as the erenumab-aooe new user cohort.

Table 2 provides the 95% confidence interval estimates for various potential risk estimates of the three cardiovascular outcomes (0.2%, 0.5%, 1%, 3%, 5%, 20%, and

30%) based on the projected sample size described above for erenumab-aooe, other mAbs targeting the CGRP pathway, and onabotulinumtoxinA. The risk of acute MI and stroke is expected to be relatively rare across all new user cohorts, while the risk of hypertension is expected to be common.

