#### 8.7.2.3 Descriptive Analysis

### 8.7.2.3.1 Description of Study Enrollment

Selection of cohort members will begin by identifying all patients with at least one prescription order for erenumab-aooe, other mAbs targeting the CGRP pathway, selected anti-epileptic medications, and onabotulinumtoxinA, between 17 May 2018 through 31 May 2020 (or, the most recent data available in MarketScan®). Cohort members who meet the inclusion/exclusion criteria for the study will be included in the final analytic data files. Attrition for all four cohorts will be described in a flow chart (Figure 1).

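### Hypertension algorithm 3 cannot confirm diagnoses made near the end of data, and Kaplan-Meier censoring at that date does not correct the understatement

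*Protocol*

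**What the plan says.** Section 8.3.4 lists five algorithms for new-onset hypertension, for which "individuals with a prior history of hypertension during the baseline period will be excluded". Algorithm 1 is a single diagnosis, the definition also given in section 8.3.2. Algorithm 2 adds an antihypertensive fill within 30 days after the diagnosis. Algorithm 3 instead requires "discontinuation of the study medication within 90 days after diagnosis".

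Section 8.2.5 recognises discontinuation once a gap above the allowed 30 days is met, and dates it at the end of the last supply with a 60-day extension. The comment under Section 5 of the checklist in Appendix B describes the allowance as 30 + 60 = 90 days.

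Entry runs "between 17 May 2018 through 31 May 2020" (8.7.2.3.1), and the study period runs "to 31 May 2020 (or the latest release date for the MarketScan" claims release (8.2.1). The enrolment criterion looks only backwards: "One year of continuous enrollment (ie, complete medical and pharmacy coverage) prior to and including the index date" (8.2.2.1). Follow-up ends at the outcome, disenrollment or end of study (8.2.5). Cumulative incidence is one minus the Kaplan-Meier function (8.7.2.4, written out for acute MI).

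For patients with treated baseline hypertension, section 8.3.4 also looks at "changes in medication dosage or initiation of new anti-hypertensive medications within 90 days after initiation of the study medication". That window starts at the index date.

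**The concern.** Kaplan-Meier censoring works when an event is known at the moment it happens. An algorithm 3 event is not: whether a diagnosis on a given day counts depends on what is seen up to 90 days later, plus any time needed to recognise the gap. Near the end of a patient's data that later information is missing. The diagnosis fails the definition and the patient is carried as event-free up to the censoring date, so the days remain in the risk set although an event on them can be confirmed only in part or not at all.

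At stake is the absolute risk of hypertension followed by stopping study medication. Estimating hypertension risk is a primary objective (7.1), and the error runs in the reassuring direction.

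**Working it through.** **Inputs.** Counts through January 2020 (8.5): "15212 erenumab-aooe users", "17239 galcanezumab-gnlm or fremanezumab-vfrm users" and 9,242 onabotulinumtoxinA users. Projections to 31 May 2020: 20,000, 23,000 and 13,000. From 31 January to 31 May 2020 is 121 days. From 17 May 2018 to data end is 745 days; for the other antibodies, from the first approval on 14 September 2018, it is 625.

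**The plan's projections.** Two full quarters at 15% give 15,212 × 1.15² = 20,118, 17,239 × 1.15² = 22,799 and 9,242 × 1.15² = 12,223. The first two match; the third falls short of 13,000. Growth over the four months actually left (1.15 to the power 4/3) gives 18,328, 20,770 and 11,135, used below as a lower accrual set.

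**Assumptions.** Even entry before and after 31 January 2020; no disenrollment; diagnoses followed by stopping at 10% per year; stopping dates spread evenly over 90 days; follow-up not cut at discontinuation; accrual in patients without baseline hypertension as in the whole cohort.

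**Follow-up F.** Share entering after January: 1 − 15,212/20,000 = 23.9%; likewise 25.0% and 28.9%. Mean F for erenumab: 0.2394 × 60.5 + 0.7606 × (121 + 745)/2 = 344 days. Other antibodies: 0.2505 × 60.5 + 0.7495 × (121 + 625)/2 = 295. OnabotulinumtoxinA: 325.

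**Chance of confirmation.** For a diagnosis r days before data end it is min(r, 90)/90. If a further 30 days are needed to see the gap, replace r by r − 30 (not below zero). Summed over r, 45 person-days per patient are lost, or 75 with the extra wait.

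**Loss on follow-up day t** = 45 × (density of F just after t) / P(F > t), where that density is flat over the window. For erenumab:
- t = 0: 45 × 0.2394/121 = 8.9%.
- t = 121: 45/(745 − 121) = 7.2%.
- t = 365: 45/(745 − 365) = 11.8%.

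The average over the first 365 days is 9.1%. The true 12-month risk is 1 − exp(−0.10) = 9.5%. The estimate is 1 − exp(−0.10 × 0.909) = 8.7%, a relative loss of 8.7%.

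**Relative understatement of 12-month risk with censoring at data end:**

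| | Erenumab | Other mAbs | OnabotulinumtoxinA |
|---|---|---|---|
| Algorithm 3, no extra wait | 8.7% | 11.0% | 9.3% |
| Same, lower accrual | 8.0% | 10.1% | 8.0% |
| Algorithm 3, 30-day wait | 14.4% | 18.2% | 15.2% |
| Same, lower accrual | 13.4% | 17.0% | 13.4% |
| Algorithm 2, fills even over 30 days | 3.0% | 3.7% | 3.2% |

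Simulated Kaplan-Meier estimates agree to within about one percentage point. When the at-risk period is ended one confirmation window early, the simulated 12-month risk returns to its true value within simulation error.

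**Person-time in the last w days** = E[min(F, w)]/E[F]. Erenumab, w = 90: (0.7606 × 90 + 0.2394 × 56.5)/344 = 24%, where 56.5 = (90²/2 + 31 × 90)/121 is the mean of min(F, 90) among late entrants.

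| w | Erenumab | Other mAbs | OnabotulinumtoxinA |
|---|---|---|---|
| 90 days | 24% | 28% | 25% |
| 120 days | 31% | 36% | 32% |
| 180 days (90 + 90) | 43% | 50% | 44% |

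**The case against.** The strongest defence is that the protocol already ends follow-up at end of data and uses a right-censored estimator. That holds for the antihypertensive-change measure, where a change is seen when it happens. With 17.8% or 21.5% of patients cut short and an assumed 90-day risk of 10%, Kaplan-Meier simulation returns 10.0%. Nothing in the protocol says that patients cut short are scored as unchanged. The remark in section 8.7.2.2 that an absent claim means absence concerns how claims are read, not time after follow-up ends. The unnamed estimator for that measure can be left to the SAP. The defence does not reach algorithm 3, whose event status depends on the future.

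Two further objections stand. Algorithm 3 is one of several supplementary definitions. And the person-time shares measure exposure to possible non-confirmation, not bias; they serve here only as the cost of the fix.

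A reader might draw three stronger conclusions that the documents do not support:
- **That about a fifth of patients are affected.** The projections do put (20,000 − 15,212) × (90/121)/20,000 = 17.8% of erenumab users within 90 days of data end, with 18.6% and 21.5% in the other two cohorts. At the stated 15% growth per quarter it is 1 − 1/1.15 = 13.0%. These shares count index dates, whereas algorithm 3's window starts at diagnosis.
- **That worsening of existing hypertension is understated.** Algorithm 3 excludes patients with baseline hypertension.
- **That cohort comparisons are distorted.** The losses imply a spurious ratio of (1 − 0.087)/(1 − 0.110) = 1.03 for erenumab against other antibodies, and 1.01 against onabotulinumtoxinA. The anti-epileptic cohort has no count, and the gated comparisons cover only acute MI and stroke.

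**Conclusion.** The point holds for algorithm 3 and, to a smaller degree, for algorithm 2. Under the protocol's own estimator, 12-month cumulative incidence by algorithm 3 is understated by roughly 8-11% in relative terms, or 13-18% if 30 more days must pass before the gap is seen. Algorithm 2 loses about 2-4%.

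The 10% yearly rate and the even spread of stopping dates are assumptions. The relative loss depends little on the rate: for erenumab it is 9.1% in the limit of rare events against 8.7% at 10% per year. It depends more on when stopping occurs and on how discontinuation is recognised, which section 8.2.5 and Appendix B describe differently. Disenrollment was left out; it brings a patient's data end forward and would add to the loss.

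Severity is minor. The affected figures are descriptive, the main hypertension definition is sound, and the 90-day antihypertensive-change measure needs no correction.

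**What to change.** In section 8.3.4, end the at-risk period for a qualifying algorithm 3 diagnosis one full confirmation window before the patient's end of enrolment or end of data. The window is 90 days plus the discontinuation gap. For algorithm 2, end it 30 days before. Count events and person-time only within that period. First reconcile the discontinuation rule in section 8.2.5 with the 30 + 60 = 90 days in the Appendix B checklist, because the length of the window depends on it.

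The cost is a changed censoring date in the programs and a wider interval for algorithm 3, which gives up about 24-28% of its person-time for a 90-day window, 31-36% for 120 days and 43-50% for 180 days. Algorithm 1 is unchanged.

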### 8.4 Data Sources

This analysis will utilize data from the MarketScan® Commercial and Medicare Supplemental medical claims database, which represents the medical experience of insured employees and their dependents for active employees, early retirees, individuals who continue their insurance coverage under the Consolidated Omnibus Budget

Reconciliation Act, and Medicare-eligible retirees with employer-sponsored medical supplemental plans. The underlying insured population from which the data are drawn is geographically diverse across the US (47% - South, 18% - North, 17% - West, 20% - North Central), 52% of plan participants are male, and 89% are enrolled in fee-for-service plans. These databases are Health Insurance Portability and Accountability (HIPAA) compliant, de-identified, and have been described in previous studies (Velentgas et al, 2006; Walker et al, 2004). The data undergo audits and quality control procedures by the insurer at regular intervals.

The Marketscan® databases contain fully adjudicated eligibility, pharmacy, procedure, and medical claims data for patients enrolled in a large US health plan (IBM Watson, formerly Truven Healthcare). The health plan provides coverage for physician, hospital, and prescription drug services and captures medical claims or encounter data from all available health care sites (inpatient hospital, outpatient hospital, emergency room, physician's office, surgery center, etc.) for virtually all types of provided services. Each facility inpatient admission record contains information on up to sixteen diagnoses (outpatient records contain up to four diagnoses), recorded with ICD-10-CM diagnosis codes and up to sixteen procedures (outpatient records allow for only one procedure) recorded with ICD-10-CM procedure codes, Current Procedural Terminology (CPT), or HCPCS codes. Data are linked at the patient level by a unique identifier that is consistent across services, health plans, and time, and, so, patients can be tracked over multiple years even if they switch health plans when working with a particular employer. Laboratory test results can be linked to the medical and pharmacy claims data for a limited subpopulation of enrollees within the Marketscan® databases. Undiagnosed conditions, and lifestyle and biometric factors (eg, smoking status) are not well captured in claims data. Data are captured when close to 100% of claims have been paid, which results in a lag time between date of service and date of payment of about 3-6 months.

Claims for pharmacy services are typically submitted electronically by the pharmacy at the time prescriptions are filled. The following pharmacy claims data allow for longitudinal tracking of medication refill patterns and changes in medications used:

- NDC or HCPCS
- Medication brand name
- Generic product identifier
- Medication strength
- Quantity prescribed

- Days of supply
- Fill date

This analysis will also utilize data from the Marketscan® Medicaid Database, which contains the pooled healthcare experience of more than 44 million Medicaid enrollees, covered under fee-for-service and managed care plans, across multiple states. It includes information on inpatient admissions and services, outpatient services, and prescription drug claims, as well as information on enrollment, long-term care, and other medical care. In addition to standard demographic variables such as age and gender, the Marketscan® Medicaid Database also includes valuable information such as ethnicity, service and provider type, Medicare eligibility, and other federal aid.

#### 8.5 Study Size

Based on recent analyses (Amgen Study 20200218) to evaluate the rate of hypertension in migraine patients, the following number of patients with a migraine preventive treatment were identified within the Marketscan® Early View claims database from May 2018 through January 2020:

- 15212 erenumab-aooe users
- 17239 galcanezumab-gnlm or fremanezumab-vfrm users
- 9242 onabotulinumtoxinA users

These migraine preventive treatment users were required to be 18-64 years of age, have a diagnosis for migraine based on ICD-10-CM diagnosis codes or one prescription order for a triptan/ergot in the prior 12 months, continuous enrollment in the claims database for at least 12 months prior to the index date, and no prior prescription for any medication targeting the CGRP pathway. These counts were generated before the February 2020 approval of eptinezumab-jjmr. Assuming a conservative 3-month growth rate of 15%, the expected number of new users during the study period (17 May 2018 – 31 May 2020) will be ~20 000 new users of erenumab-aooe, ~23 000 new users of other mAbs targeting the CGRP pathway, and ~13 000 new users of onabotulinumtoxinA. While new users of the SOC migraine preventive medications (anti-epileptics) were not evaluated, other analyses in the Optum electronic health record database suggest that this new user cohort will be at least as large as the erenumab-aooe new user cohort.

Table 2 provides the 95% confidence interval estimates for various potential risk estimates of the three cardiovascular outcomes (0.2%, 0.5%, 1%, 3%, 5%, 20%, and

30%) based on the projected sample size described above for erenumab-aooe, other mAbs targeting the CGRP pathway, and onabotulinumtoxinA. The risk of acute MI and stroke is expected to be relatively rare across all new user cohorts, while the risk of hypertension is expected to be common.

#### Table 2. 95% CI Estimates and Half-widths for a Range of Cardiovascular Outcome Values, Based on a Sample Size of 20 000 Erenumab-aooe Users, 23 000 Users of Other mAbs Targeting the CGRP Pathway and 13 000 Onabotulinumtoxin A Users

	Erenumab-aooe N = 20 000		Other mAbs Targeting the CGRP Pathway N = 23 000		OnabotulinumtoxinsA N = 13 000	
CV Outcome (%)	95% CI	Half-width of Cl	95% CI	Half-width of Cl	95% CI	Half-width of Cl
0.20	0.14, 0.26	0.06	0.14, 0.26	0.06	0.12, 0.28	0.08
0.50	0.40, 0.60	0.10	0.41, 0.59	0.09	0.38, 0.62	0.12
1.00	0.86, 1.14	0.14	0.87, 1.13	0.13	0.83, 1.17	0.17
3.00	2.76, 3.24	0.24	2.78, 3.22	0.22	2.71, 3.29	0.29
5.00	4.70, 5.30	0.30	4.72, 5.28	0.28	4.63, 5.37	0.37
20.0	19.5, 20.6	0.55	19.5, 20.5	0.52	19.3, 20.7	0.69
30.0	29.4, 30.6	0.64	29.4, 30.6	0.59	29.2, 30.8	0.79

Abbreviations: CI: confidence interval; mAbs: monoclonal antibodies; CGRP: calcitonin gene-related peptide

Table 3 provides a range of detectable risk ratios for two outcomes of interest (acute MI and stroke), assuming 80% power, alpha-level of 0.05, and equal number of patients in each medication cohort, if a comparative analysis of the erenumab-aooe cohort to each comparator cohort (other mAbs targeting the CGRP pathway, selected SOC migraine preventive medications (anti-epileptics), or selected onabotulinumtoxinA ) were conducted. This table assumes a background rate of acute MI of 0.15 per 100 PYs and a background rate of stroke of 0.60 per 100 PYs (Gill et al, 2020).

 Table 3. Detectable Risk Ratios for Two Cardiovascular Outcomes

	Total Population in Each Medication Cohort						
Outcome	N = 13 000	N = 17 000	N = 20 000	N = 25 000			
Acute MI	2.10	1.94	1.85	1.75			
Stroke	1.58	1.51	1.46	1.41			

The estimates provided above are for informational purposes only. The final sample size for the study will change due to the criteria applied during the conduct of the protocol.

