We will assess the following variables during the baseline period: demographics, *a priori* defined covariates of interest, including comorbidities, concomitant medications, and risk factors for the outcomes, and cohort descriptors identified empirically from the most prevalent diagnoses, procedures, and prescriptions.

Study Sample Size

In a recent study of the MarketScan® Early View database, a total of 15212 erenumab-aooe users, 17239 users of other mAbs targeting the CGRP pathway, and 9242 users of onabotulinumtoxinA were identified from May 2018 through January 2020. Assuming a conservative 3-month growth rate of 15%, the expected number of new users during the study period (17 May 2018 – 31 May 2020) will be ~20 000 new users of erenumab-aooe, ~23 000 new users of other mAbs targeting the CGRP pathway, and ~13 000 new users of onabotulinumtoxinA.

Based on these sample size estimates, the 95% CIs for a cumulative incidence for stroke of 0.50% are (0.40%, 0.60%) for erenumab-aooe, (0.41%, 0.59%) for other mAbs targeting the CGRP pathway, and (0.38%, 0.62%) for onabotulinumtoxinA medication users. The 95% CIs and half-widths of the CIs were estimated across a range of cumulative incidence values, assuming varying population sizes, for all three cardiovascular outcomes of interest (hypertension, acute MI, and stroke).

If a comparative analysis is conducted (assuming 20 000 patients in the erenumab-aooe cohort and 20,000 patients in the comparator cohort, a background rate for stroke of 0.60 per 100 person-years (PYs), and an alpha-level of 0.05), a risk ratio of 1.46 would be detected with 80% power. Detectable risk ratios, assuming different population sizes and background rates, were estimated for acute MI and stroke.

• Data Analysis

Baseline characteristics, including the most prevalent diagnoses, procedures, and medication class prescriptions will be summarized for the four study cohorts. Descriptive statistics using mean and standard deviation or median and 25th/75th percentile estimates for continuous variables and number and percentages (n, %) for categorical variables will be used to examine patient characteristics.

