### **Descriptive Analyses**

### Estimating the Cumulative Distribution of a Right-Censored Outcome

Following the notation by Cole et al (Cole et al, 2015) and Brookhart (Brookhart, 2019), let  $T_i$  be the continuous random variable for the time from treatment initiation to acute MI

for the  $i^{th}$  patient, and let *t* represent the realization (ie, a specific value) of  $T_{i.}$  The cumulative incidence (ie, risk) of the acute MI outcome at time *t* is the complement of the Kaplan-Meier survival function,

$$R(t)=1-S(t)=\Pr(T_i < t).$$

The entire function over time is of interest, but the cumulative incidence of acute MI at times t=6 months, t=1 years, and t=2 years after the start of treatment will also be estimated.

The naïve, unadjusted cumulative incidence of the outcome, R(t), subject to rightcensoring by *C*, can be conveniently estimated with the following estimating function:

$$\widehat{Pr}(T < t) = \frac{1}{n} \sum_{i=1}^{n} \frac{\Delta_i I(T_i < t)}{Pr(\Delta_i = 1)},$$

where  $\Delta = l(T < C)$  is an indicator that the patient was uncensored. In the denominator  $Pr(\Delta_i = 1)$  implies that censoring is non-informative (ie,  $C \perp T$ ), and, so, the cumulative incidence curve that is initially estimated assumes that censoring occurs at random.

In addition to estimating the cumulative incidence, the incidence rate, overall, and by selected baseline characteristics, with 95% confidence intervals based on the Poisson distribution, will also be estimated.

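### Table 2 and the abstract give uncensored binomial precision at full cohort size, although the planned risks are right-censored Kaplan-Meier estimates and new-onset hypertension drops part of the cohort

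*Protocol*

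**What the plan says.** Protocol section 8.5 presents Table 2, headed "95% CI Estimates and Half-widths for a Range of Cardiovascular Outcome Values, Based on a Sample Size of 20 000 Erenumab-aooe Users", as intervals "based on the projected sample size described above for erenumab-aooe, other mAbs targeting the CGRP pathway, and onabotulinumtoxinA", that is, 20 000, 23 000 and 13 000 patients. These are all new users expected between 17 May 2018 and 31 May 2020. The abstract repeats one row as an expected result: "the 95% CIs for a cumulative incidence for stroke of 0.50% are (0.40%, 0.60%) for erenumab-aooe".

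The estimator is defined in section 8.7.2.4: "The cumulative incidence (ie, risk) of the acute MI outcome at time *t* is the complement of the Kaplan-Meier survival function". It is to be reported at 6 months, 1 year and 2 years, and the same methods apply to stroke. For new-onset hypertension, section 8.3.4 has the risk "evaluated at 1 month, at 2 months, at 3 months, at 6 months, and at 12 months" and narrows the population: "When evaluating new onset hypertension, individuals with a prior history of hypertension during the baseline period will be excluded".

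Section 8.2.1 closes the study period on 31 May 2020, or at the latest database release, for which no date is given. Section 8.2.5 ends follow-up at the outcome, at disenrollment or at the end of the study period. Below Table 3 the protocol adds that the estimates are informational and that the final sample size will change with the criteria applied.

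**The concern.** A binomial half-width at full N is right only if every patient is observed to the time point or to an earlier event. Here the cohorts accrue until the day follow-up stops, so late entrants are censored early by design. For new-onset hypertension, the N in the table also counts people whom section 8.3.4 removes.

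The cumulative incidences are a primary, ungated objective, and Table 2 with its abstract extract is the protocol's only statement of how precisely they will be known. If the printed intervals ignore censoring, a reader will expect tighter estimates at 12 and 24 months than the design can give, and will not see that one cohort has no 24-month data on the stated dates.

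**Working it through.** **1. Reproduce Table 2.** Half-width = 1.96 × √(p(1−p)/N).
- p = 0.30, N = 20 000: 0.635 points (printed 0.64)
- p = 0.20, N = 20 000: 0.554 (printed 0.55)
- p = 0.005, N = 20 000: 0.098 (printed 0.10); N = 23 000: 0.091 (0.09); N = 13 000: 0.121 (0.12)

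All 21 half-widths reproduce this way. No time point, censoring or exclusion enters.

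**2. Follow-up window.** From 17 May 2018 to 31 May 2020 is 745 days (24.5 months). The first other mAb was approved on 14 September 2018, leaving at most 625 days (20.5 months).

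**3. Share able to reach 12 months.** The protocol does not give the accrual pattern, so three are used for erenumab:
- Even accrual: (745 − 365)/745 = 51%.
- Later-weighted: 15 212 of 20 000 evenly to 31 January 2020, the rest evenly over the last 121 days: 0.7606 × (745 − 365)/(745 − 121) = 46%.
- The protocol's 15% growth per 3 months, projected backwards: 1/1.15⁴ = 57%.

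Other mAbs, even accrual: (625 − 365)/625 = 42%.

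The growth pattern is favourable. Carried back to launch it leaves 1/1.15^(745/91.3) = 32% of the cohort already present on the first day.

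**4. Kaplan-Meier precision, administrative censoring only.** With constant hazard λ and G(u) the share with potential follow-up of at least u, the Greenwood variance at time t is (1−p)² × ∫₀ᵗ λ du / (N·S(u)·G(u)).

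For a rare outcome with even accrual over T days, the ratio to the binomial variance is (T/t) × ln(T/(T−t)), which can be checked by hand:
- Erenumab, 12 months: (745/365) × ln(745/380) = 1.374; square root 1.17; 0.098 × 1.17 = 0.115.
- Erenumab, 24 months: (745/730) × ln(745/15) = 3.99; square root 2.00; half-width about 0.20.
- Other mAbs, 12 months: (625/365) × ln(625/260) = 1.50; square root 1.23; 0.091 × 1.23 = 0.112.

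Full integral, erenumab, N = 20 000 (half-widths in percentage points):

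| Risk, time | Table 2 | Growth | Even | Later-weighted |
|---|---|---|---|---|
| 0.50%, 6 months | 0.098 | 0.105 | 0.105 | 0.108 |
| 0.50%, 12 months | 0.098 | 0.113 | 0.115 | 0.120 |
| 0.50%, 24 months | 0.098 | 0.133 | 0.195 | 0.205 |
| 30%, 6 months | 0.635 | 0.685 | 0.683 | 0.707 |
| 30%, 12 months | 0.635 | 0.741 | 0.752 | 0.785 |

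The widening is about 7-11% at 6 months and 16-24% at 12 months. The abstract's stroke interval of 0.40-0.60%, read at 12 months, becomes about 0.38-0.39% to 0.61-0.62%. For other mAbs the 24-month risk is not estimable by 31 May 2020, because 625 days is less than 730.

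**5. Exclusion of baseline hypertensives.** The excluded share e is not in the documents, and 10-40% is an assumption. The half-width scales by 1/√(1−e). At 30% and 12 months for erenumab, this runs from 0.741/√0.9 = 0.78 to 0.785/√0.6 = 1.01, against 0.64 printed. MI and stroke are unaffected by this step.

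**The case against.** The table contains no arithmetic slip. Its title states the sample sizes, it names no time point, and the text calls the figures informational and warns that N will change. That is fair, and a reader should not infer a calculation error or a broken guarantee. But the caveat speaks of N changing. It does not say that censoring was ignored, and the intervals remain too narrow at exactly 20 000 patients. Twelve months is an inference, supported by its being a planned time point for every outcome and by the feasibility rate of 3.56 per 10 person-years giving 1 − exp(−0.356) = 30%, a row of the table. That rate is not stated to exclude baseline hypertensives, so 30% need not be the new-onset risk.

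The data end may also move. Section 8.7.2.2 speaks of about 2.5 years of maximum follow-up, whereas the stated dates allow 745/365.25 = 2.04. With even accrual to 31 May 2020 and six further months of follow-up, about 76% reach 12 months and the half-widths are 0.66 at 30% and 0.101 at 0.50%, close to Table 2. This stands as mitigation. It does not correct figures tied to a 31 May 2020 projection.

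Finally, no gate or sample size rests on Table 2, and the actual intervals will be reported. This limits the consequence to the stated expectation.

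Stronger readings do not hold. Counting only patients with 12 months of data (N about 10 000) would suggest widening by 1.41, but censored patients still contribute to Kaplan-Meier. Claims that hypertension intervals nearly double need assumed disenrollment and treatment-stopping rates that the protocol does not give. Nor is every time point materially affected by censoring: with even accrual the widening is about 1% at 1 month and 3% at 3 months.

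**Conclusion.** The point holds. Table 2 and the abstract's stroke intervals describe fully observed cohorts, which the planned estimator will not have on the stated dates. From administrative censoring alone, erenumab half-widths at 12 months are about 0.74-0.78 rather than 0.64 at 30%, and 0.113-0.120 rather than 0.10 at 0.50%. The effect is small at 6 months and larger at 24 months (about 0.13-0.21 at 0.50%), where other-mAb users have no data by 31 May 2020. These figures rest on a constant hazard and three accrual patterns. Disenrollment would widen them and a later data cut would narrow them. For new-onset hypertension N is too large at every time point. The range of 0.78-1.01 at 30% and 12 months depends on the assumed 10-40% excluded. The loss of precision is modest at 12 months, and it is a matter of honest reporting rather than feasibility.

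**What to change.** Recompute Table 2 and the abstract intervals with the Greenwood variance of one minus Kaplan-Meier at named time points for each outcome, using expected index-date accrual to the stated data end. If a later release is intended, give its date and add the corresponding figures. Base the hypertension rows on the cohort without baseline hypertension. State the assumed baseline hypertension share and disenrollment as ranges. Mark the 24-month other-mAb entry as not estimable unless the data end moves.

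The cost is one recalculated table and one abstract sentence. The stated precision becomes modestly less favourable, and neither the design nor the number of patients changes.
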